14 INVESTIGATIONAL PLAN

The IRBs will be notified of the Post-Approval condition to follow these subjects and the study will be converted from IDE#120046 to a Post-Approval Study status under P150038. The study data will be collected electronically.

14.1 LTF Follow Up Periods Years 2 – 5 Post Treatment

The treatment long term safety and effectiveness follow up will be completed annually from Year 2 through Year 5 post treatment under this protocol. It should be noted that at these visits, the CRST assessments will be performed and scored by the site neurologist.

The following evaluations should be performed at Year 2, Year 3, Year 4 and Year 5:

- Review of medications
- Physical exam

- CRST – Assessed by site evaluator
- QUEST questionnaire should be completed by the subject
- Adverse events

14.2 Exit from the study for reason of alternative treatment

In this study, subjects who opt for alternative treatments for Essential Tremor (not including medication change) at any point in the follow-up period will be exited from the study after completing the required study examinations. The last set of evaluations prior to alternative therapy is considered the last study visit. The reason(s) for study exit will be noted on the Case Report Forms. No analyses of post alternative treatment changes are planned.

14.3 Study Requirements and Visit Schedule

All subjects who were part of the original IDE, IDE # G120246 in either the ET002 pivotal trial, or the ET002CA (Note: inclusive of all patients treated under the original Pivotal Study, those treated under the Continued Access approval, and those treated as part of the 1.5T Coil cohort) will be rolled into this PAS study at whatever stage of follow-up is coming due. Follow-up will be continuous from the time of treatment to the Year 5 visit.

Subjects who have not attained Month 12 will continue their schedule of visits as (originally scheduled):

- 1 Week \pm 3 days
- 1 Month \pm 7 days,
- 3 Month \pm 14 days
- 6 Months \pm 21 days
- 12 Months \pm 4 month

| Table 4.2.2.3.2—1 | | | | | | | | | |
|---|-----------|----------|-----------|-------|--------|---------|---------|---------|----------|
| Summary of Study Schedules and Measurements | | | | | | | | | |
| | Screening | Baseline | Treatment | 1 Day | 1 Week | 1 Month | 3 Month | 6 Month | 12 Month |
| Consent | X | | | | | | | | |
| Eligibility Evaluation with labs | X | X | | | | | | | |
| Medications | X | X | X | X | X | X | X | X | X |
| 30 day meds stabilization | | X | | | | | | | |
| Medical History | X | | | | | | | | |
| Physical Exam | X | X | | X | X | X | X | X | X |
| Neurological status | X | | X | X | X | X | X | X | X |
| CRST | X | | | | | X | X | X | X |
| QOL (QUEST) | X | X | | | | X | X | X | X |
| PHQ-9 | X | | | | | X | X | X | X |
| CT | X | | | | | | | | |
| MR | | X | X | | | | | | X |
| Treatment | | | X | | | | | | |
| Adverse Events | | | X | X | X | X | X | X | X |
| Forms “UB-04 (In Patient subjects) or CMS-1500 (Out Patient subjects) | | X | X | X | X | X | X | X | X |
| Exit Form | | | | | | | | | X |

The table below summarizes the long-term study visit schedule and procedures.

The study visits are as follows:

Year 2 ± 4 Month;

Year 3 ± 4 Month,

Year 4 ± 4 Month,

Year 5 ± 4 Month.

Table 4.2—2 Summary of Study Schedules and Evaluations

| | Year 2 4 Month | Year 3 \pm 4 Month | Year 4 \pm 4 Month | Year 5 \pm 4 Month |
|-----------------------|---------------------------|--|--|--|
| Physical Exam | X | X | X | X |
| CRST | X | X | X | X |
| QOL (QUEST) | X | X | X | X |
| ET medications | X | X | X | X |
| Adverse Events | X | X | X | X |
| Exit Form | X | X | X | X |

Note:

1. To enable subject(s) retention in the Long Term Follow-up study as well as to ensure patient welfare and safety (in full compliance with all applicable patient consent regulation(s) and their corresponding IRB approvals), all participating sites should make every effort to maintain frequent contact with subjects (at least 3 to 4 times a year) to encourage visit compliance and keep them engaged for patient retention.

In the event a patient miss their scheduled visit to complete the study visit requirements, sites should at the very least inquire with subject to provide an overall assessment of their safety and of their tremor in full compliance with all applicable patient consent regulations and rights, and or schedule another clinical visit even if it is outside the visit window.

15 DATA ANALYSIS PLAN

15.1 Safety

Adverse events will be recorded and categorized according to severity, relationship to procedure and relationship to device. All AEs will be assessed for their relationship to the study device or procedure. Standard Code of Federal Regulation definitions for Serious Adverse Events (SAEs) and Unanticipated Adverse Device Effects (UADEs) will be used in assessment of AEs.

It is the responsibility of the investigator to document all AE's occurring during the course of the study. At each visit, the investigator will evaluate AE's. AE's not previously documented in the study will be recorded on the Adverse Event Log within the CRF. The nature of each event, date and time (when appropriate) of onset, outcome, frequency, maximum intensity, action taken, expectedness, and causal relationship will be recorded. AEs already documented in the CRF (i.e., at a previous assessment) and designated as

‘ongoing’, should be reviewed at subsequent visits as necessary. If these have resolved, the documentation in the CRF should be completed including an end date for the event.

Standard Code of Federal Regulation (CFR) definitions for Serious Adverse Events (SAEs) will be used for evaluation of adverse events.

SAE [§803.3(aa)(1)] is an injury or illness that:

- *causes death*
- *is life threatening, even if temporary in nature;*
- *results in permanent impairment of a body function or permanent damage to a body structure; or*
- *necessitates medical or surgical intervention to preclude permanent impairment of a body function or permanent damage to a body structure.*

All AEs (related or unrelated) meeting the criteria for an SAE require notification of the sponsor and the reviewing IRB as soon as possible, with subsequent completion of additional paperwork provided by the sponsor fully documenting the course of the event, all treatments, and final outcome. Initial reporting of an SAE should be made to the sponsor no later than two (2) working days after the PI learns of the incident. AE's that do not affect the safety or overall well-being of the subject, are mild/moderate in nature, are estimated to be temporary in duration even though the exact end date may not be determined *a priori* (e.g., eye twitch increased from baseline) may be presented and discussed with DSMB to determine their final classification status as a serious or non-serious adverse event.

Standard Code of Federal Regulation (CFR) definitions for Unanticipated Adverse Device Effects (UADEs) will be used for evaluation of this type of adverse event.

UADE [§812.3(s)] means any serious adverse event on health or safety or any life-threatening problem or death caused by, or associated with, a device, if that effect, problem, or death was not previously identified in nature, severity, or degree of incidence in the investigational plan or application (including a supplementary plan or application), or any other unanticipated serious problem associated with a device that relates to the rights, safety, or welfare of subjects.

Any UADEs will be reported to the Sponsor and to the reviewing IRB as soon as possible. However, in no event must this report be made later than two (2) working days after the PI learns of the incident.

15.2 Data Safety Monitoring Board

A Data Safety Monitoring Board will be used to review all AE's on the study. Their role is to evaluate all AE's that occur throughout the study and determine if they are in fact related to the ExAblate, or some other cause. Investigators will monitor all treatments for any AE's, and consider the following questions for AEs in the Test Arm:

- *Was the adverse event serious?*

- *Was the adverse event life-threatening, caused a disability, required or prolonged hospitalization, or caused death?*
- *Was the adverse event device related?*
- *Was the adverse event unexpected?*
- *Is there an unreasonable risk in continuing the trial?*

Adverse Events meeting all the above conditions would require reporting to the FDA, stopping the study pending the results of further investigation, and FDA approval to restart the study.

All adverse events will be assessed for their relationship to the study device or procedure. Standard Code of Federal Regulation (CFR) definitions for SAEs and UADEs will be used in assessment of adverse events.

15.3 Efficacy

Primary effectiveness will be evaluated using the CRST scored by the site assessor based upon patients where unilateral ExAblate thalamotomy was performed. Secondary efficacy will be collected using the QUEST.

15.4 Subject Health Status

The results from the physical exams will be recorded in the CRFs and will be presented.

15.5 Statistical Considerations and Sample Size

There is no statistical consideration or sample size for this study. All ExAblate treated subjects who were treated under ET002 or ET002-CA will be included in this study, starting at the next scheduled study visit date; ET002-CA was FDA approved under IDE Supplement G120246/S07.

15.6 Missing Data

Analyses will be performed on both observed and data with missing values imputed per the method of last observation carried forward (LOCF) where data for missing visits is assigned the value of the previous visit.

NOTE:

All Demographic, Screening, Baseline, Treatment and some amount of Follow-up data are collected under ET002 or ET002-CA and these data will be used in coordination with that collected under this protocol.

15.7 Statistical Analysis Plan.

The analysis will be performed based upon the Statistical Analysis Plan (“SAP”) procedures as defined for the pivotal study (FDA Approval of SAP under IDE

Supplement G120246/S06). Please note, however, that for the PAS, all analyses will be performed using the site assessor data only.

15.8 Subject Confidentiality

Subject confidentiality will be maintained throughout this study, including all publications. Data collected and entered into the CRFs are the property of the study sponsor. Representatives from the study sponsor or authorized sponsor representatives, the Institutional Review Board, Data Safety Monitoring Board, Ethics Committee or other regulatory bodies may receive copies of the study records and may review medical records related to the study.

16 PMA P150038 Specific Questions

What serious or unexpected adverse events may occur in the long-term (up to 5 years) after receiving treatment for the proposed indication?

No known device-related SAEs/UADEs are expected over the follow-up of subjects through Year 5 based on historical literature on thalamotomies as published in the literature. The ExAblate procedure is a one-time procedure. However, per this study protocol, safety data will be collected through Year-5 as planned. The full safety data will be reported to the Agency as required.

In the long-term (5 years), will favorable Composite Tremor/Motor Function scores compared to the baseline be sustainable among the patients who have received the treatment?

Based on historical outcomes as published in the literature, it is reasonable to believe that the Composite Tremor/Motor Function improvement will be maintained through follow-up. However, because this cohort of subjects is the first group of subjects to be treated using the ExAblate 4000 device and for many investigators, this was the first hands-on experience in using the device, it is reasonable to anticipate that there may be some patients who do not sustain their improvement over the duration of this study. With the accumulation of user expertise in using the ExAblate 4000, it is expected that the composite Tremor/Motor score outcomes will be sustainable over long durations. It is the purpose of this long-term follow-up protocol to capture the very long term data of the composite Tremor/Motor scores for this cohort of subjects.

17 RISK ANALYSIS

Worldwide, over 12,7000 treatments have been performed to date with the MR guided FUS ExAblate body system. Risk analysis for InSightec ExAblate systems/clinical investigations has been conducted as part of previously approved FDA IDE submissions

(G930140, G990151, G990184, G990201, G000203, G010225, G020001, G020182, G050177, and G060023, G070022, G080009, G080206, G100108, G100127, G100169, G120246, G120017, G140018, G140082, G160021, P040003 and subsequent supplements, P110039 and P150038). This data has been re-examined by the study sponsor and it has been concluded that this risk analysis has limited applicability to the proposed clinical investigation. The key consideration here is the fact that this proposed study is conducted with an ExAblate Neuro system that is completely different from the body system. This system is referred to internally as the Neuro system. However, in principle, the body and neuro systems have the same purpose, namely to coagulate soft tissue within the body by means of MR guided high intensity focused ultrasound.

There are no additional new risks anticipated under this study. All the risks were described under the original treatment protocol and are still active for this protocol. No new treatments are performed here as this is strictly a long-term observational study.

17.1 Criteria for Removal from the Study

The investigator may withdraw subjects from the study as is deemed necessary or deemed to be in the best interests of the subject, such as,

- continued noncompliance with the protocol or study visits,
- severe illness or disability during the study for non-study issues,
- pursuit of subsequent alternative treatment for the same condition, or
- development of intolerable side effects where continued follow-up becomes too burdensome.

In addition, a subject may also choose to exit the study at any time, but will be strongly encouraged to participate in the follow-up visits for safety reasons (continued monitoring of subject safety). Sites should make every effort to contact all subjects for study follow-up to encourage visit compliance. Sites should keep a log of dates of attempted contact and results. After 3 unsuccessful attempts at contact (e.g., by telephone or email) and sending 1 certified letter to solicit their visit compliance a subject may be considered lost to follow-up.

17.2 Data Safety Monitoring Board

A Data Safety Monitoring Board will be used to review all recorded AEs on the study. Note that only ET-disease, device and procedure-related adverse events will be recorded. Their role is to evaluate all recorded AEs that occur throughout the study and determine if they are in fact related to the original ExAblate procedure, or some other cause. Investigators will capture all adverse events, and consider the following questions:

- *Was the adverse event serious?*
- *Was the adverse event life-threatening, caused a disability, required or prolonged hospitalization, or caused death?*

- Was the adverse event device related?*
- Was the adverse event unexpected?*
- Is there an unreasonable risk in continuing the trial?*

Adverse Events meeting all the above conditions would require reporting to the FDA, stopping the study pending the results of further investigation, and FDA approval to re-start the study. Following the DSMB review of the event, and if in the opinion of the DSMB, a modification of the study protocol were necessary to provide adequate protection to future study participants, the modification would be implemented prior to reinitiating the investigation. Any such amendment would be reported to the IRB and FDA for their respective approvals to re-start the study as it is required by the applicable regulations.

All recorded adverse events will be assessed for their relationship to the study device or procedure. Standard Code of Federal Regulation (CFR) definitions for SAEs and UADEs will be used in assessment of adverse events.

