12.1 Primary Endpoints

12.1.1 Safety

Safety of ExAblate will be determined by an evaluation of the incidence and severity of device / treatment related complications from the treatment day visit through ALL study follow ups through Year 5. Adverse events (type, frequency, severity) are expected to be similar to those of previous studies using ExAblate Neuro for Thalamotomy

Recorded adverse events will be reported and categorized by investigators as definitely, probably, possibly, or unrelated to the device or procedure. Events which are not considered to be possibly or probably caused by the device are not required to be reported here.

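### The long-term follow-up protocol (ET002-LTF) gives incompatible rules on which adverse events are recorded, so procedure-related events and events a site calls unrelated can drop out of the Year 5 safety data

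*Protocol*

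**What the plan says.** The follow-up protocol sets the scope of adverse event (AE) recording in four places.

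- **Section 12.1.1 (Safety)** sets a device-only threshold: "Events which are not considered to be possibly or probably caused by the device are not required to be reported here". The sentence before it uses a wider scale: "Recorded adverse events will be reported and categorized by investigators as definitely, probably, possibly, or unrelated to the device or procedure". The primary safety endpoint, defined in the same section, is the incidence and severity of complications related to the device or the treatment, from the treatment day through Year 5.
- **Section 15.1 (Safety)** asks for everything: "It is the responsibility of the investigator to document all AE's occurring during the course of the study". It also says where events go: "AE's not previously documented in the study will be recorded on the Adverse Event Log within the CRF". For serious events (SAEs) it adds: "All AEs (related or unrelated) meeting the criteria for an SAE require notification of the sponsor".
- **Section 15.2 (Data Safety Monitoring Board)** has the same breadth: "A Data Safety Monitoring Board will be used to review all AE's on the study".
- **Section 17.2 (Data Safety Monitoring Board)** restricts recording: "Note that only ET-disease, device and procedure-related adverse events will be recorded". Soon after it says: "Investigators will capture all adverse events, and consider the following questions". It gives the board the task of deciding whether recorded events are related to the original procedure.

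Section 15.7 has the follow-up data analysed by the pivotal SAP. SAP section 10.5 tabulates all AEs, including by relation to treatment, and plots the AE-free percentage over time. In the parent protocol, section 6.6 requires all AEs to be documented.

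**The concern.** Safety through Year 5 is a primary endpoint of the follow-up study, and the sections tell sites different things about which events to enter. Two sites that follow the text in good faith could build different databases from the same clinical experience.

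Three things are at stake. The first is whether the endpoint is complete for events related to the procedure but not attributed to the device. The second is whether the safety board can review relatedness, given that an event may be screened out at the site by that same judgement. The third is whether the SAP's all-AE displays can be produced on a consistent basis and read alongside the parent stage. Section 14.3 describes follow-up as continuous from treatment to Year 5, and subjects who have not reached Month 12 carry on under this protocol.

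**Working it through.** The plan states no figure on this point, so there is none to reproduce. The check sets the rules side by side for each type of event.

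| Event, as judged by the site | 12.1.1 | 15.1 and 15.2 | 17.2, restricting sentence | 17.2, capture-all sentence | In the primary endpoint? |
|---|---|---|---|---|---|
| 1. Device-related | Required | Recorded | Recorded | Captured | Yes |
| 2. Procedure-related, not device-caused | Not required | Recorded | Recorded | Captured | Yes |
| 3. Related to ET disease only | Not required | Recorded | Recorded | Captured | Only if reclassified |
| 4. Unrelated, non-serious | Not required | Recorded | Not recorded | Captured | Only if reclassified |
| 5. Unrelated, serious | Not required | Recorded, sponsor and IRB notified | Not recorded | Captured | Only if reclassified |

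**Step 1: is there a reading that reconciles the text?** The natural attempt is that sites capture everything in source records but enter only related events in the CRF. Section 15.1 rules this out, because it puts each new AE on the log inside the CRF. No section says which rule takes precedence.

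**Step 2: does the conflict reach the endpoint?** Row 1 is the same under every rule. Row 2 is not: it lies inside the endpoint, yet 12.1.1 does not ask for it. The class is not marginal. Section 18 describes the pivotal events other than those considered transient and unrelated as related to the procedure or the thalamotomy.

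**Step 3: does it reach the safety board?** Under 17.2 the board evaluates recorded events. If a site follows the restricting sentence, rows 4 and 5 are not recorded, so a mistaken call of unrelated cannot be corrected from the recorded data. If a site follows 12.1.1, row 3 may be missing as well. SAE notification under 15.1 still brings row 5 to the sponsor and the IRB. What is unclear is whether those events also enter the CRF dataset and go to the board.

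**Step 4: does it reach the analysis?** SAP section 10.5 uses all AEs. Rows 2 to 5 enter its tables and AE-free curve under 15.1, rows 2 and 3 under the restricting sentence of 17.2, and none of the four need enter under 12.1.1. The parent stage used the 15.1 rule, so a change in AE rate after a subject moves into follow-up could reflect the recording rule and not the patients.

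**Step 5: size.** This would need AE counts by relatedness for the pivotal or follow-up cohort. Section 18 says only that many pivotal events were considered unrelated and gives no count. The effect cannot be computed.

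**The case against.** The strongest reply is that targeted capture was intended and is reasonable. Sections 15.1 and 15.2 largely repeat the parent protocol, and 15.2 still speaks of the Test Arm and of monitoring treatments although none are given. Section 17.2 was adapted to the follow-up study and carries the restriction. In an observational study with no new treatment and an endpoint limited to related complications, leaving out unrelated non-serious events is defensible. Section 12.1.1 is also permissive: it waives reporting and forbids nothing.

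Two further points narrow the consequence. Section 17.2 includes events related to ET disease, so under that rule the board does see them and can reclassify them. And neither 12.1.1 nor 17.2 withdraws the duty in 15.1 to notify SAEs whatever their attribution, so a reader who infers that every misattributed event is lost goes further than the text allows.

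All of this stands as a limit on the consequence. None of it removes the contradiction. Even if 17.2 is taken as the intended rule, it disagrees with 12.1.1 on procedure- and ET-related events, with 15.1 on what goes on the log, and with its own statement that all events are captured.

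**Conclusion.** The contradiction is real and the sections should be reconciled. Its demonstrable reach is threefold: procedure-related events inside the primary safety endpoint can be left out under 12.1.1; events that a site ties to neither device, procedure nor ET may not reach the board; and the SAP's all-AE outputs have no consistent input and no assured comparability with the parent stage. The size is unknown. The conclusion assumes that treatment-related complications in the endpoint include procedure-related ones, which fits the device-or-procedure scale in 12.1.1.

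Three stronger readings are tempting but not supported.

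- **That Year 5 incidence is biased downward as a matter of course.** Events judged device-related are recorded under every rule. The count falls only if sites omit procedure-related events under 12.1.1, or if the board would have upgraded an event that the site dismissed. The documents do not show how often either would happen.
- **That a numerical bound is lost.** For zero events in the 56 ExAblate subjects of section 18, the one-sided 95% upper limit is 1 − 0.05^(1/56) = 0.052. But 56 is the pivotal ITT arm. Sections 14.3 and 15.5 also bring in the continued-access and 1.5T coil subjects, and sections 13.1.2 and 14.2 take some subjects out. The endpoint also runs from the treatment day, and section 18 already reports related events, so zero events cannot describe it.
- **That 12.1.1 exempts definite device events because it names only possible and probable ones.** The preceding sentence lists definite events, and the threshold is plainly a lower limit.

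**What to change.** State one recording rule and use it in 12.1.1, 15.1, 15.2 and 17.2. At a minimum, every SAE regardless of attribution, and every AE related to the device, the procedure or ET, should be entered in the CRF and go to the safety board. Change the device-only threshold in 12.1.1 so that it matches the endpoint. State which set of AEs feeds the SAP section 10.5 tables and the AE-free curve and, if it is narrower than in the parent stage, say how the two periods will be presented.

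The simplest version is to record all AEs, classify attribution afterwards, and tabulate related events as a subset. That agrees with 15.1, with the parent protocol and with the SAP. A narrower rule is acceptable if it meets the minimum above and is stated the same way throughout.

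The cost is a wording change in the follow-up protocol and the AE form instructions, plus modest extra AE entry at the annual visits. It is best done early, because events that were never recorded may not be recoverable later.
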